Endpoints	For this proof of concept study, the primary endpoints will be changes in Vibration Perception Threshold and Quantitative Sensory Testing between baseline and end of treatment. Secondary endpoints will be changes in nerve conduction velocity (NCV) of the sural nerve and amplitude from baseline to end of treatment, changes in Skin Perfusion Pressure (SPP) from baseline to end of treatment, change in Pain Intensity using the 11-point Numeric Pain Rating Scale (NPRS) from baseline to end of treatment, change from baseline in Brief Pain Inventory (BPI) and Brief Fatigue Inventory (BFI), change from baseline in Patient Global Impression of Change (PGIC), change from baseline in Hospital Anxiety and Depression Scale (HADS), and changes from baseline in neuropathy and foot ulcer specific quality of life instrument (NeuroQoL).
	Safety will be assessed through review of Adverse Event (AE) reports and concomitant treatments and medications. All concomitant drug or non-drug treatments used during the study will be recorded. Safety outcomes will be assessed at the interim visits and the end of study visit.
Study Procedures	Following informed consent and assessment of eligibility, subjects will complete Section A-History of the Michigan Neuropathy Screening Instrument (MNSI) with Section B- Physical Assessment completed by the site. A measurement of the depth of the right foot will be measured from the most inferior aspect of the medial malleolus to the plantar aspect of the foot when residing on the treatment pad. The depth should not be more than 8cm for eligibility. A finger stick will be performed on the subject to obtain a baseline HbA1c value (A1C Now [®] test kit) and subjects will complete a Urine Drug Screen in office. Subjects will undergo the Ankle-Brachial Index (ABI), Venous Insufficiency Assessment, and Pain Phase evaluation (at least 10 subjects in each of the 2, 3, and 4 pain phases will be enrolled). For subjects of child bearing potential a urine pregnancy test will be obtained.

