Subject adherence (compliance with twice daily treatment with the study device) will be assessed during the interim visits by viewing the usage meter on each device, and upon completion of the treatment period at the Day 121 visit by the research staff reading and recording the number displayed on the study device usage meter. The usage meter will read 0.0 at Enrollment and upon randomization and will increase by 0.5 for each complete 30-minute treatment. A subject with complete adherence will be expected to have a usage meter reading based upon their response date.

Subjects will be instructed to return all unused DACs at the end of treatment visit. Each treatment session requires one new DAC, thus in the course of 120 days of treatment, the subject will utilize up to 240 DACs. If a subject is determined to be a non-responder at Day 91, they will utilize 180 DACs per PEMF device (360 total).

M. Protocol Adherence

Strict adherence to all specifications laid down in this protocol is required for all aspects of the study conduct. If protocol modifications are necessary, all alterations that are not solely of an administrative nature require a formal protocol amendment.

If an investigator has deviated from the protocol in order to eliminate an immediate hazard to subjects or for other inevitable medical reasons, the investigator shall document all such deviations, including the reasons thereof, and immediately submit the documentation to the sponsor and to the IRB if required.

N. Concomitant Medications

All concomitant drug and non-drug treatments as well as the frequency of administration and indication for the treatment will be recorded in the subject's chart. Additions to the subject's therapeutic regimen (agent, dose, frequency of administration) for treatment of diabetic peripheral neuropathy (other than the introduction of PEMF therapy) will not be allowed through Day 121 of the study. Subjects will be allowed to continue administration of prn medications on an *ad lib* basis. Subjects may choose to reduce or discontinue opioid or other drug therapies during the treatment period of the study.

It is important to record the reason why each analgesic is being taken by the subject, specifically analgesics taken for treatment of pain associated with diabetic neuropathy. Analgesics taken for other reasons, e.g., headache, will be collected through recording of concomitant medications in the subject's chart.

1. Allowed Medications

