Subjects will be allowed to continue their regimen of analgesic medications from the time of the Screening Visit through and including the Day 121 visit. In this context, "analgesic medications" refers to medications prescribed and administered for the treatment of pain, and includes but is not limited to anticonvulsants, opioids, nonsteroidal anti-inflammatory agents, anti-depressants and muscle relaxants. As such, this includes medications taken on an "as needed" (prn) basis as well as those medications taken on a regular schedule. Subjects may continue to take prn medications on an *ad lib* basis in response to their pain experience. Subjects who experience increased pain during the study will be instructed to increase the self-administration of their prescribed prn analgesic(s). Subjects may choose to reduce or discontinue prn opioid or other analgesic drug therapies during the treatment period of the study, and will be specifically instructed to do so by the investigator if their pain remits.

Medications prescribed for other indications are allowed and will be recorded as concomitant medications. Low dose aspirin (acetylsalicylic acid) 81 mg is allowed if taken for cardiac or vascular prophylaxis.

2. Prohibited Medications/Treatments

The following medications and therapeutics are prohibited throughout the study:

- Systemic steroids or topical steroids on the lower extremities
- Transcutaneous electrical neurostimulators (TENS units)
- Implanted neurostimulators
- Local injections
- Intrathecal infusion
- Acupuncture
- Surgery

V. WITHDRAWAL PROCEDURES

If a subject is withdrawn from study participation, the subject's enrollment in the study will terminate, study device application will be discontinued and no further data will be collected on the subject. Efforts will be made to perform all assessments scheduled for the Day 121 Visit prior to subject withdrawal.

A subject may be withdrawn from further study participation under the following circumstances:

- At the subject's request.
- Noncompliance with the protocol by the subject.
- Non-Responder at Day 91
- Adverse Event (decision to be removed from study made by either the investigator or subject). The investigator must notify the sponsor immediately if a subject is withdrawn because of an AE.
- Decision by the investigator or sponsor that termination is in the subject's best medical interest or administrative decision for a reason other than that of an AE.

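### Prn analgesic use is directed to follow pain, but the planned NPRS comparison takes no account of it and the diary does not record it, so the active-sham pain difference may be attenuated

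*Combined protocol and SAP*

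**What the plan says.** **Medication rules.** Protocol Section IV.N.1 (Allowed Medications) ties prn intake to pain in both directions. For rising pain: "Subjects who experience increased pain during the study will be instructed to increase the self-administration of their prescribed prn analgesic(s". For falling pain, subjects may reduce or stop prn analgesics and "will be specifically instructed to do so by the investigator if their pain remits". Section IV.N (Concomitant Medications) says of "Additions to the subject's therapeutic regimen (agent, dose, frequency of administration) for treatment of diabetic peripheral neuropathy" that, PEMF aside, they "will not be allowed through Day 121 of the study". Its next sentence reads "Subjects will be allowed to continue administration of prn medications on an" ad lib basis. It then says subjects may choose to reduce or discontinue drug therapy.

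**Recording.** Section IV.N has the "frequency of administration and indication for the treatment will be recorded in the subject's chart", and concomitant medications are reviewed at every visit. The Appendix C diary has a daily pain score and a weekly PGIC, and no medication field.

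**Endpoints and analysis.** According to the synopsis, "the primary endpoints will be changes in Vibration Perception Threshold and Quantitative Sensory Testing between baseline and end of treatment". Among the secondary endpoints is "change in Pain Intensity using the 11-point Numeric Pain Rating Scale (NPRS) from baseline to end of treatment". Section VI.C tabulates change from baseline to Day 120, and separately to the last observation, in randomised subjects. It gives pairwise differences between arms with 95% confidence intervals. No formal testing is planned, but p-values below 0.05 will be described as statistically significant. Section VI contains no summary of analgesic use by arm, no rule for pain scores recorded under changed use, and no sensitivity analysis. It defers detail to a separate SAP, which was not available for this review, and says that the SAP will be built on Section VI.

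**The concern.** The pain comparison in a randomised withdrawal study depends on pain returning in subjects switched to sham. Here returning pain is to be met with more analgesic, and remission with less. If subjects follow this, the recorded NPRS on sham rises less than it otherwise would, and the NPRS on active improves less. Both effects shrink the difference between arms.

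At stake is how the secondary pain result is read. A small difference could mean little effect of the device, or an effect partly offset by analgesic use, and the planned outputs would not separate the two. A saving in analgesic use would also go unreported as a comparison between arms, although the protocol's background section cites a post-operative study in which PEMF lowered opioid consumption against sham.

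**Working it through.** The plan gives no figure to reproduce: Section VI.E describes 40 patients as a convenience sample, with no effect size, SD or power. The check therefore sets the passages side by side and then gives an illustration.

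**Step 1: where NPRS comes from after randomisation.** Appendix A schedules a clinic NPRS at Screening, Enrollment and Day 61, and at Days 75 and 91 only for subjects who have not yet responded. The Day 105 and Day 121 procedure lists contain none. Once a subject is randomised, the diary is the only scheduled NPRS source.

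**Step 2: whether analgesic use can be matched to those scores.** Chart review takes place at Days 61, 75, 91, 105 and 121, so at intervals of 14 to 16 days. It can show a change in medication over an interval. It cannot reliably show whether a given daily score followed extra doses.

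**Step 3: illustrative size.** All inputs are assumptions; the documents give none of them.

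- p_S = share of sham subjects who raise prn use: 0.3 to 0.5
- p_A = share of active subjects who raise it: 0.1
- r = NPRS relief from the extra use: 0.5 to 1.0 point

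Attenuation = (p_S − p_A) × r

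- Few or no prn users: p_S and p_A near 0, so about 0
- Low case: (0.3 − 0.1) × 0.5 = 0.1 point
- High case: (0.5 − 0.1) × 1.0 = 0.4 point

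This leaves out reductions on active. If a quarter of active subjects also cut prn use and their scores rose by 0.5 point, that would add 0.25 × 0.5 = 0.125 point in the same direction.

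**Step 4: set against the precision of the study.** The 95% interval half-width for a difference in means is 1.96 × SD × √(2/n), with SD assumed.

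| n per arm | SD 1.5 | SD 2.0 | SD 2.5 |
|---|---|---|---|
| 20 (all 40 randomised) | 0.93 | 1.24 | 1.55 |
| 10 | 1.31 | 1.75 | 2.19 |

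An attenuation of up to 0.4 point is smaller than the sampling error in every cell. Unlike sampling error, it has a known direction if prn use follows pain as instructed.

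**Step 5: the two medication sections.** Section IV.N bars additions in dose or frequency and then lets prn use continue ad lib. Section IV.N.1 limits the instructed increase to prn drugs already prescribed. Read together, they can mean that the regimen is fixed while prn intake may vary. Two tensions remain: additions not allowed against an instruction to increase, and a choice to reduce against a specific instruction to reduce.

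**The case against.** **Limited consequence.** NPRS change is one of several secondary endpoints in an unpowered proof-of-concept study whose primary endpoints are VPT and QST. The bias is towards no difference, so it would not create a false benefit. Comparing pain under analgesics as actually taken is also a legitimate question. All of this stands, and it is why the planned analysis should stay and the addition be only supportive.

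**The SAP may deal with it, and the data are partly captured.** The omission can be shown only for Section VI. Analgesic use is recorded in the chart, and the synopsis says all recorded data will be listed. This stands in part. Listings are not a by-arm summary, Section VI is the declared basis for the SAP, and an analysis plan cannot restore daily intake that the diary never collected.

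A reader might infer four stronger claims that the documents do not support:

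- *That pain differences are masked.* No inclusion criterion requires a prn prescription. With few prn users the attenuation is close to zero.
- *That the two medication sections flatly contradict each other.* The ad lib sentence largely reconciles them. What is left is wording that sites could apply differently.
- *That 0.1 to 0.4 point is 10 to 40% of the effect.* The 1-point figure in the protocol is a within-subject response threshold. The protocol states no between-arm effect to divide by.
- *That the responder criterion biases the comparison.* A 1-point drop can follow a change in medication, and the criterion sets no condition on analgesic use. But it is applied before randomisation, so it can dilute the enrichment in both arms without biasing active against sham.

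**Conclusion.** The point holds in a limited form. Prn intake is directed to move with pain, the analysis in Section VI takes no account of it, and the only scheduled post-randomisation NPRS source does not record it. The active-sham NPRS difference may therefore be attenuated by an unknown amount: 0 to about 0.4 point under the assumptions shown, and somewhat more if reductions on active are counted. The direction rests on subjects following the instructions. The size rests on prn use and relief that the documents do not give. The primary endpoints are outside this point. It is worth correcting because the remedy is cheap and daily intake that is not collected during the study cannot be reliably recovered later.

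**What to change.** 1. Keep the planned NPRS analysis as it is.
2. Add a table by arm of the change in prn and scheduled analgesic use for diabetic neuropathy from randomisation to Day 121.
3. Prespecify one supportive NPRS analysis that does not credit scores recorded under analgesic use above the subject's level at randomisation. For example, count response as lost if NPRS returns to baseline or analgesic use rises above that level. The SAP should state how that level is determined.
4. Add a daily diary field for the number of prn analgesic doses taken for neuropathic pain. A count is needed because a yes/no entry would not show extra doses in someone who already takes prn medication every day.
5. The sponsor should reconcile the wording of Sections IV.N and IV.N.1 on increases and reductions. Which clinical rule applies is for the sponsor to decide.

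The cost is slightly more diary burden, one table, one supportive analysis and a short text change.

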	• is definitely not associated with the study device administered and is readily explained by other events or diagnoses.						

Each AE will also be independently judged by the investigator in terms of severity. The following definitions will be used for these severity assessments.

Mild:	The event is transient (<48 hours) or causes mild discomfort; no medical intervention/therapy is required				
Moderate:	The event results in mild to moderate limitation in activity – some assistance may be needed; no or minimal medical intervention/therapy is required				
Severe:	The event results in marked limitation in activity, assistance is usually required; medical intervention/therapy is required and hospitalization is possible				

Each AE will also be independently judged by the investigator in terms of seriousness. A serious adverse event (SAE) is defined as any untoward medical occurrence that:

- Results in death, or
- Is life-threatening,

Note: The term "life-threatening" in the definition of "serious" refers to an event in which the subject was at risk of death at the time of the event; it does not refer to an event which hypothetically might have caused death if it were more severe.

- Requires inpatient hospitalization or prolongation of existing hospitalization,
- Results in permanent impairment of a body function or permanent damage to a body structure,
- Is a congenital anomaly/birth defect,
- Necessitates medical or surgical intervention to preclude any one of the outcomes listed in this definition.

All SAEs must be reported *immediately* (within 24 hours of knowledge of the event) by telephone and fax to the following:

Sponsor Medical Contact – [name], MD; Regenesis Biomedical Inc.

[contact]; [contact]; [contact]

The investigator will follow up with a written description of the SAE submitted to the sponsor within 3 days, including the results of the SAE investigation and any treatment(s) provided.

All adverse events will be followed until resolution or until the investigator assesses the subject's status has returned to normal.

B. Anticipated Adverse Device Effects Associated with Provant Therapy System

Anticipated adverse events associated with PROVANT[®] Therapy System² and the procedures and medicines used in the study are as follows:

- Device fails to operate
- Warmth or burning at treatment site
- Skin reaction at treatment site (tingling, pins-and-needles, rash, blisters, swelling, dry skin, redness, numbness)

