- Increased bleeding at surgical site
- Chilliness
- Headache
- Malaise
- Nausea
- Abdominal or chest wall discomfort
- Muscle cramps
- Excessive menstruation
- Failure to reduce pain or an increase in pain

² Reported at least once since market launch in 2004.

C. Unanticipated Adverse Device Effect (UADE)

Unanticipated Adverse Device Effect means any serious adverse effect on health or safety or any life-threatening problem or death caused by, or associated with, a device, if that effect, problem, or death was not previously identified in nature, severity, or degree of incidence in the protocol or informed consent form, or any other unanticipated serious problem associated with the device that relates to the rights, safety, or welfare of subjects. The protocol will contain all of the anticipated Adverse Events that could be associated with the study.

All UADEs must be reported *immediately* (within 24 hours of knowledge of the event) by telephone and fax to the following:

Sponsor Medical Contact – [name], MD; Regenesis Biomedical Inc.; [contact]; [contact]; [contact]

The investigator will follow up with a written description of the UADE submitted to the sponsor within 3 days, including the results of the UADE investigation and any treatment(s) provided.

Any UADE occurring up to the date of the final Follow-up Visit will be followed until it resolves, the investigator assesses the subject's status to have returned to baseline, or until the investigator feels that the event is stable and chronic.

The investigator shall submit to the reviewing IRB a report of any UADE occurring during an investigation as soon as possible in accordance with the IRB submission guidelines, but in no event later than 10 working days after the investigator first learns of the effect.

XI. INVESTIGATOR'S FILES/RETENTION OF DOCUMENTS

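### Section V ends all data collection at withdrawal, but Section X requires every adverse event to be followed to an endpoint; both cannot be met for a subject who leaves with an open event

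*Combined protocol and SAP*

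**What the plan says.** **Section V (Withdrawal Procedures).** When a subject is withdrawn, enrollment ends, use of the device stops and "no further data will be collected on the subject". The next sentence softens this: "Efforts will be made to perform all assessments scheduled for the Day 121 Visit prior to subject withdrawal". The listed reasons for withdrawal include an adverse event and remaining a non-responder at Day 91. For the former, "The investigator must notify the sponsor immediately if a subject is withdrawn because of an AE".

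**Section VI (Statistical Considerations).** The Safety Analysis Set is described as followed through the randomized phase or up to the point of withdrawal.

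**Section X.A (Adverse Events).** "All adverse events will be followed until resolution or until the investigator assesses the subject's status has returned to normal". For serious events there is a 24-hour report, and then: "The investigator will follow up with a written description of the SAE submitted to the sponsor within 3 days".

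**Section X.C (UADE).** "Any UADE occurring up to the date of the final Follow-up Visit will be followed until it resolves", or until the investigator judges that the subject is back to baseline or that the event is stable and chronic.

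**The concern.** An event that leads to withdrawal, or is still running when a non-responder is discharged at Day 91, falls under two opposing instructions. Section V tells the site to stop collecting data. Section X tells it to go on until the event reaches an endpoint. Section IV.M demands strict adherence to every specification in the protocol, so the site has no stated freedom to choose between them. Different sites (up to four are planned) may resolve the conflict differently.

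What is at stake is the completeness of safety outcomes. The efficacy comparison and the sample size are not affected.

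**Working it through.** The plan gives no figure to reproduce on this point and no arithmetic applies. The check sets the rules side by side and follows the subjects they govern.

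**Does either rule yield to the other?**

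| Rule | Scope | When it ends | Exception for the other rule |
|---|---|---|---|
| Section V | all data on a withdrawn subject | at withdrawal | none |
| Section VI | follow-up of the Safety Analysis Set | end of randomized phase or withdrawal | none |
| Section X.A | all adverse events | resolution or return to normal | none |
| Section X.C | UADEs up to the final visit | resolution, return to baseline, or stable and chronic | none |

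Section VI sides with Section V, so the conflict does not rest on one stray sentence.

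**Which subjects are caught?**

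1. *Event resolved before withdrawal.* Both rules are met and there is no conflict.
2. *Withdrawn because of an event that is still open.* Section X requires follow-up and Section V forbids recording it.
3. *Day 91 non-responder with an open event.* The same conflict arises, because this exit is on the Section V list.
4. *Event that begins just after exit.* Section V bars recording it. For example, a Day 91 non-responder completes the Day 121 procedures (Section IV.I). These include a repeat biopsy for anyone biopsied at baseline (Section IV.K, item 15). The subject is then terminated at the end of that same visit (Section VI.B). A complication of the biopsy would usually show only afterwards. Appendix E recognizes such a hazard: it excludes certain patients because of their risk of a non-healing venous ulcer after biopsy.

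**What is already captured at exit?**

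- The Day 121 assessments, attempted before withdrawal, include an adverse event review (Section IV.K, item 16). This is best effort and records status at exit only.
- The sponsor is told at once of a withdrawal for an adverse event.
- Serious events are described in writing within 3 days, including the results of the investigation and treatments given. That is an early report and need not contain the final outcome.
- The investigator judges causality and severity for each event (Section X.A), so an event known at exit can carry both.

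**What would be lost under Section V?**

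- The end date, which Section III.C says will be assessed for each event.
- Later worsening. Section VI.D counts each subject once at the worst severity, so a rise in severity after exit would not reach the table.
- A later change to serious. The Section X.A criteria include hospitalization and permanent impairment, either of which can follow an event that was not serious at exit.
- Any revised causality judgement. Section VI.D counts each subject at the strongest relationship.
- Events with onset after exit, as in case 4.

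The first four items apply to cases 2 and 3. For the severity and seriousness tables the bias runs one way, because missing later information can only leave an event at a lower category than it finally reached.

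**The case against.** The strongest reply is that little is lost in practice. An event that causes withdrawal is by definition known beforehand. It has been reported to the sponsor, judged for severity and causality, and, if serious, described in writing. Section VI.D plans counts by severity, relationship, seriousness and discontinuation; it plans no table of outcome or resolution. A site might also sensibly treat Section X, the specific safety rule, as governing.

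Much of this stands. A reader might infer that events leading to discontinuation would drop out of the tables, or appear without a relationship to the device. The documents do not support that: such events would still be tabulated with the judgement made at or before exit.

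A reader might also be tempted to size the problem by assuming a non-response rate and applying it to the 40 planned subjects. That would count people who leave, when only those with an open or later event are affected, and the documents give neither a response rate nor an adverse event rate.

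Two parts of the reply do not stand. The exit safeguards capture status at departure, not what follows. And nothing in the text gives Section X priority, while the Section VI description of the safety set points the other way.

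**Conclusion.** The contradiction is real and is in the current text. For a subject withdrawn with an open adverse event, including a Day 91 non-responder, Sections V and X cannot both be obeyed. If a site follows Section V, end dates, later worsening, revised causality and events appearing after exit go unrecorded. The worst-severity and serious-event summaries could then understate harm. Events known at exit remain counted.

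The number of subjects affected cannot be estimated from the documents. The conclusion assumes only that at least one subject leaves with an unresolved event, or has one soon after exit, and that the site reads Section V literally. This is a modest defect in safety reporting. The primary endpoints are untouched.

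**What to change.** Reconcile Sections V, VI and X in one amendment:

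- **Section V:** limit the stop on data collection to non-safety data. State that adverse events open at withdrawal continue to be followed and recorded as Section X already requires, subject to the subject's agreement. That condition is needed because Section VII leaves subjects free to withdraw at any time for any reason and Section V lists the subject's request as a route out.
- **Day 91 non-responders:** say expressly that the same provision covers them. State also whether, and for how long, events beginning after the exit visit are recorded, since a rule for open events alone would not catch a complication of the exit biopsy.
- **Section VI:** align the description of the Safety Analysis Set, so that follow-up of open events after withdrawal belongs to the safety data.

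There is no need to open efficacy collection after withdrawal; this point gives no argument for it. The cost is a short text amendment and a small amount of recording. The duty to follow open events already exists in Section X, although Section X does not say how subjects are to be contacted (telephone is mentioned there only for reports to the sponsor).
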